4.2 Study Schematic

4.3 Schedule of Assessments

Table 1: Schedule of Assessments

Procedure	Screening Visit (3-28 days)¹	Baseline Visit (Randomization)¹	Onset of moderate or severe migraine²	During Treatment 15, 30, 45, 60 and 90 minutes Post-Dose	During Treatment 2, 3, 4, 6, 8 hours Post- Dose	During Treatment 24 hours Post-Dose	During Treatment 48 hours Post- Dose	End of Treatment Visit
Eligibility Assessments								
Informed Consent	X							
Inclusion/Exclusion Criteria	X	X						
Medical History	X							
Prophylactic Migraine Medication/ Concomitant Medication ³	X	X						X
Assessment of Migraine History (Signs and symptoms) paper source ¹⁴	X							
Safety Assessments								
Physical Examination	X							X
Vital Signs/Physical Measurements ⁴	X	X						X
Clinical Safety Laboratory Testing ⁵	X							X

Procedure	Screening Visit (3-28 days)¹	Baseline Visit (Randomization)¹	Onset of moderate or severe migraine²	During Treatment 15, 30, 45, 60 and 90 minutes Post-Dose	During Treatment 2, 3, 4, 6, 8 hours Post-Dose	During Treatment 24 hours Post-Dose	During Treatment 48 hours Post-Dose	End of Treatment Visit
ECG	X							X
Pregnancy Test ⁶	X	X	X					X
Adverse Event and Serious Adverse Event Assessment ⁷	X	X	X	X	X	X	X	X
Sheehan Suicidality Tracking Scale ⁸	X	X						X
Clinical Drug Supplies/Study Supplies								
Randomize ⁹		X						
Dispense Study Medication		X						
Administer 1 dose of study medication ¹⁰			X					
Return unused study medication								X
eDiary returned/reviewed for completeness ¹¹								X
Efficacy Assessments¹²								
Assessment of migraine pain ¹³			X	X	X	X	X	

Procedure	Screening Visit (3-28 days)¹	Baseline Visit (Randomization)¹	Onset of moderate or severe migraine²	During Treatment 15, 30, 45, 60 and 90 minutes Post-Dose	During Treatment 2, 3, 4, 6, 8 hours Post-Dose	During Treatment 24 hours Post-Dose	During Treatment 48 hours Post-Dose	End of Treatment Visit
Assessment of Migraine Symptoms (photophobia, phonophobia, and nausea - eDiary) ¹³			X	X	X	X	X	
Functional Disability Scale ¹³			X	X	X	X	X	
MQoLQ (Migraine Specified Quality of Life Questionnaire) ¹³						X		
Preference of Medication ¹³						X		

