¹ **Screening/Baseline Phase** will be 3 - 28 days. The **Baseline Visit** may be scheduled but should only occur *after* all screening procedures are complete, patient meets inclusion/exclusion criteria, and lab test results have been received by the site.

² Patients will use eDiary to answer questions about their migraine symptoms upon experiencing a moderate/severe migraine headache. The patient will administer pre-dispensed study drug if 1) the headache remains moderate or severe; 2) the patient has completed all required migraine assessment questions in the eDiary, including their current most bothersome migraine symptom, and 3) the patient has not already taken prohibited medications (see protocol section 5.4).

³ Patients should keep track of their concomitant medications throughout the study and report them to the study personnel at the End of Treatment Visit. Any medication taken for recurrent headache should be documented. Use of concomitant medications after randomization, including rescue medications, will be recorded by the patient on a paper diary and reported to the site.

⁴ Height will only be captured at the Screening Visit. Weight body temperature, respiratory rate, blood pressure and heart rate will be collected at all time points where indicated. Sitting arterial systolic and diastolic blood pressure and pulse rate will be measured.

⁵ All Screening Visit laboratory test results must be received prior to Baseline Visit.

⁶ A serum pregnancy test will be completed at Screening and End of Treatment Visits as part of the standard laboratory tests (if appropriate). Confirmatory urine pregnancy test for WOCBP should be completed on site at Baseline Visit and any subsequent visits for confirmation at the Investigator's discretion. Home pregnancy test will be provided to WOCBP after completion of baseline visit.

⁷ SAEs are reported from the time of informed consent and non-serious AEs are reported from baseline. All ongoing non-serious AEs and SAEs will be followed to resolution or until investigator deems there will be no further status change. SAE and AE's that occur during the treatment period should be reported to the site.

⁸ This scale will be clinician administered, completed on site, and will be in paper. The source document will be provided by Biohaven. The assessment period for completing the scale will be 30 days prior to Screening, and since the last visit for the remainder of the study.

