4.3.1 Screening Phase (3-28 days)

It is estimated that approximately 1415 patients will be screened to allow 1200 patients to be randomized at the Baseline visit. All patients who are screened into the study will be entered into the IWRS system. After obtaining informed consent, patients will undergo all screening procedures as detailed in [Table 1](#). After all screening procedures are complete, patients will return 3-28 days from signing informed consent to be randomized at the Baseline visit if they meet all eligibility criteria. Patients on prophylactic migraine medication are permitted to remain on therapy provided they have been on a stable dose for at least 3 months prior to randomization.

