4.3.2 Acute (Randomization) Phase (45 days)

If the patient meets all eligibility criteria they will be randomized at the Baseline Visit via the IWRS system. The patients will be provided with an eDiary. The study personnel will instruct the patient on the proper use of the eDiary and ensure proper understanding and use of the tool, prior to the patient leaving the office.

After randomization via the IWRS system, the patient will be dispensed a single dose of the double-blind study medication to take home for up to 45 days. This study medication is to be taken when a migraine attack reaches moderate or severe intensity on the numeric rating scale (NRS) as indicated in the eDiary. The patient will be instructed to take their study medication, as an outpatient, when (if) they have a migraine headache which reaches moderate or severe intensity **after they answer eDiary questions about their current pain and symptoms and identify their currently most bothersome, migraine associated, symptom (phonophobia, photophobia or nausea)**. The patient will complete an eDiary for up to forty-eight hours after taking study medication. The patient will telephone the study center immediately if a severe or serious adverse event occurs.

Patients will record efficacy data in their eDiary. This includes the following: onset time of headache, intensity of the headache prior to **and** at time of taking study medication. The patient should record all headache intensity leading up to dosing, but should not dose with study medication until the headache reaches moderate or severe intensity. Headache severity will be recorded using a four-point numeric rating scale (no pain, mild pain, moderate pain, severe pain) at the onset of the migraine and after dosing at time points of 15, 30, 45, 60, and 90 minutes and 2, 3, 4, 6, 8, 24 and 48 hours. The presence or absence of associated symptoms (nausea, photophobia, phonophobia) and ratings of functional disability (four-point scale: normal, mildly impaired, severely impaired, requires bedrest) will be recorded at the same time points as the headache severity ratings. Patients will also identify their currently most bothersome symptom before taking study medication. Patients will record the date and time study therapy was taken in their eDiary. Patients will also complete the migraine-specific quality-of-life questionnaire (MQoLQ) and preference of medication (PoM) 24 hours after

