4.3.4 End of Treatment (7 days after Treatment)

Patients will return to the study site within 7 days of study treatment (+2 days) for review of the eDiary assessment of medication compliance, and monitoring of tolerability and safety (including vital signs, laboratory tests, and electrocardiography). If a patient has NOT experienced a migraine headache of sufficient severity within 45 days after randomization, he or she will be withdrawn from the trial and instructed to return unused study medication and eDiary to the study center.

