 - ii) Detectable levels of marijuana in the drug screen are not exclusionary, if in the investigator's documented opinion the patient does not meet DSM-V criteria[15] for substance use disorder, in the investigator's documented opinion, the positive test does not signal a clinical condition that would impact the safety of the patient or interpretation of the study results.
3. Allergies and Adverse Drug Reactions
- a) History of drug or other allergy which, in the opinion of the principal investigator, makes the subject unsuitable for participation in the study
4. Sex and Reproductive Status
- a) Females of child-bearing potential who are unwilling or unable to use an acceptable contraceptive method or abstinence to avoid pregnancy for the entire study period and for 56 days after the study.
 - b) Women who are pregnant or breastfeeding. Women with a positive pregnancy test on enrollment or prior to study drug administration
5. ECG and Laboratory Test Findings
- a) Estimated glomerular filtration rate (eGFR) according to the re-expressed abbreviated (four-variable) Modification of Diet in Renal Disease (MDRD) Study equation $\leq 40 \text{ ml/min/1.73m}^2$
 - b) Corrected QT interval $> 470 \text{ msec}$ (QTc by method of Frederica), during the Screening/Baseline Phase
 - c) Left Bundle Branch block
 - d) Right Bundle Branch Block with a QRS duration $\geq 150 \text{ msec}$.

- e) Intraventricular Conduction Defect with a QRS duration ≥ 150 msec.
 - f) Serum bilirubin (Total, Direct or Indirect) $> 1 \times$ ULN (Only abnormal values of between 1-1.5x ULN may be repeated once for confirmation during the screening period.)
 - g) Neutrophil count $\leq 1000/\mu\text{L}$ (or equivalent).
 - h) AST (SGOT) or ALT (SGPT) $> 1 \times$ ULN (Only abnormal values of between 1-1.5x ULN may be repeated once for confirmation during the screening period.)
6. Other Exclusion Criteria
- a) Prisoners or subjects who are involuntarily incarcerated
 - b) Subjects who are compulsorily detained for treatment of either a psychiatric or physical (e.g., infectious disease) illness
 - c) Exposure to non-biological investigational agents (other than rimegepant) within the 30 days prior to Baseline visit.
 - d) Exposure to biological investigational agents within the 90 days prior to Baseline visit.
 - e) Score of >0 on the Sheehan Suicidality Tracking Scale for the period of 30 days prior to Screening and during the study.

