5.7.6.6 Sheehan-Suicidality Tracking Scale (S-STS)

The S-STS is a prospective, self-reported rating scale that contains 16 questions to track both treatment-emergent suicidal ideation and behaviors. In the event the subject is unavailable, the S-STS clinician-administered rating scale will be completed that contains 6 yes/no questions.

Self-reported S-STS scores are calculated as follows:

- Ideation subscale score: Sum of scores (0-4) for Questions 2-11
- Behavior subscale score: Sum of scores (0 4) for Questions 1a, (highest of 12 or any row of 16), (highest of 14 or any row of 15), 17, and 20
- Total score: Sum of the ideation and behavior subscale scores

The self-reported S-STS ideation subscale, behavior subscale, and total score will be summarized at baseline and the change from baseline (i.e., <-1, -1, no change, 1, >1) will be summarized at the end of treatment visit.

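### The End of Treatment suicidality score covers the pre-dose wait of up to 45 days, so a pre-dose event would count as change at end of treatment on a scale meant to track treatment-emergent events.

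*Protocol*

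**What the plan says.** Protocol section 4.3, Table 1, schedules the S-STS at three visits only: Screening, Baseline (Randomization) and End of Treatment. Footnote 8 gives the recall period as "30 days prior to Screening, and since the last visit for the remainder of the study".

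The intervals between these visits are set elsewhere in the protocol:

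- **Screening to Baseline** (section 4.3.1): "patients will return 3-28 days from signing informed consent to be randomized at the Baseline visit".
- **Baseline to dose** (section 4.3.2): after randomization, "the patient will be dispensed a single dose of the double-blind study medication to take home for up to 45 days".
- **Dose to End of Treatment** (section 4.3.4): within 7 days, with 2 further days allowed. SAP Table 6 (section 5.2.9) accepts a visit from 2 to 21 days after the dose for analysis.

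Protocol section 6.2.5 and SAP section 5.7.6.6 both describe the scale as following treatment-emergent ideation and behavior. The SAP summarizes scores at baseline, and "the change from baseline (i.e., <-1, -1, no change, 1, >1) will be summarized at the end of treatment visit". SAP Table 3 repeats the five change categories for the total score in all treated subjects.

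Exclusion 6e (Protocol section 5.3) bars a "Score of >0 on the Sheehan Suicidality Tracking Scale for the period of 30 days prior to Screening and during the study". Eligibility is checked at both Screening and Baseline, and section 5.7 allows no exceptions.

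**The concern.** At the Baseline Visit the tablet is handed over but not taken. Because the next S-STS is at End of Treatment and looks back to the previous visit, its score mixes days before any study drug with days after it. Nothing on the form or in the SAP tells them apart.

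The stated objective is the effect of rimegepant on this scale at end of treatment. A subject who has suicidal thoughts in week two of the wait, takes the tablet in week four and is well afterwards would appear in the table as a rise from baseline. Positive scores on such a scale are likely to be few, so one or two misdated cases could change how the safety table is read, in either arm.

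**Working it through.** **Check on the intervals.** The longest schedule is 28 days (screening) + 45 (wait) + 7 (to End of Treatment) = 80 days, and 80/7 = 11.4 weeks. This agrees with the total of about 11 weeks stated in Protocol section 4.1, so the intervals are being read as intended.

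**Recall length.** Let w be the days from Baseline to dose (0 to 45) and p the days from dose to the End of Treatment Visit (about 7; up to 9 with the allowance; 2 to 21 in the SAP analysis window).

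- Recall at Baseline = Screening to Baseline = 3 to 28 days.
- Recall at End of Treatment = w + p.
- Post-dose share = p / (w + p), which is below one half whenever w > p.

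| Wait w | p = 7 | p = 9 | p = 21 |
|---|---|---|---|
| 7 days | 7/14 = 50% | 9/16 = 56% | 21/28 = 75% |
| 15 days | 7/22 = 32% | 9/24 = 38% | 21/36 = 58% |
| 30 days | 7/37 = 19% | 9/39 = 23% | 21/51 = 41% |
| 45 days | 7/52 = 13% | 9/54 = 17% | 21/66 = 32% |

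**Typical waits.** The documents do not give the distribution of waits, so this step rests on assumptions.

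- *Constant hazard, fitted to the plan.* Protocol section 9.2 expects about 90% of randomized subjects to have a migraine in the allotted period. The daily rate is then −ln(0.10)/45 = 0.0512. The mean wait among those treated is 1/0.0512 − 45 × 0.10/0.90 = 14.5 days. With p = 7, the pre-dose part of the mean recall is 14.5/21.5 = 67%.
- *Constant hazard at the entry limits.* Two attacks per 30 days gives a mean wait of 12.6 days and 12.6/19.6 = 64% pre-dose. Eight per 30 days gives 3.7 days and 3.7/10.7 = 35%.
- *Evenly spaced attacks, randomization at a random point.* The mean wait is half the spacing. For two attacks it is 15/2 = 7.5 days, so 7.5/14.5 = 52% pre-dose. For eight it is 3.75/2 = 1.9 days, so 1.9/8.9 = 21%.

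The pre-dose part of a typical recall is therefore roughly 20% to 70%, depending on the assumption. These are ratios of mean times, not averages of individual shares.

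**Effect of the zero baseline.** SAP section 6 defines baseline as the last assessment before randomization, which for this scale is the Baseline Visit. The efficacy baseline in SAP section 5.7 is migraine onset, when the scale is not given. With exclusion 6e applied at Baseline, the baseline score is 0, so change = End of Treatment score − 0 = End of Treatment score. The categories −1 and below −1 can then be filled only by eligibility deviations. The categories 1 and above 1 together are simply any score above 0.

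**The case against.** Three stronger conclusions are tempting, and the documents do not support them.

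- **That unequal recall periods spoil the subtraction.** With baseline at 0 nothing is subtracted, whatever period the baseline covered. Unequal recall matters only if the result is read as worsening within a subject.
- **That a longer window and a zero floor produce apparent worsening by construction.** A rise still needs an event. The window is not always longer either: with p = 7, waits of 4 and 15 days give recalls of 11 and 22 days, both inside the 3 to 28 days possible at Baseline. The End of Treatment recall passes 28 days only when the wait exceeds 21.
- **That the arm comparison is biased.** Pre-dose days fall in both randomized, blinded arms. They add background and dilute any effect of the drug, but do not by themselves favor either arm.

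It can also be said that the plan already handles this. SAP section 6.2 counts adverse events from randomization, so the S-STS convention is not out of line. A subject judged at risk must have the event recorded as an AE or SAE (Protocol section 6.2.5), and AE start dates can be compared with the dose time in the eDiary. S-STS results are listed by subject (Listing 16.2.11.6).

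This answers only part of the concern. The AE route applies to subjects the investigator considers at risk, not to every non-zero item, and neither document asks for an S-STS item to be dated. The remaining objections stand: the objective is exploratory, SAP section 5.7.6.6 specifies no test, and completing a 16-question scale twice at one visit would cost too much.

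**Conclusion.** The point holds as a timing and labeling defect in an exploratory safety summary. The End of Treatment S-STS takes in the whole pre-dose wait, and the plan cannot tell a pre-dose event from a post-dose one on a scale both documents describe as treatment-emergent.

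The boundary case leaves 13% to 32% of the recall after the dose, for visits 7 to 21 days after dosing. Typical shares depend on the assumed waits. Dilution cannot be expressed in events, because the documents give no event rate. The conclusion assumes that footnote 8 is followed literally, that no unscheduled visit resets the recall, and that exclusion 6e is applied at Baseline. Pre-dose here means before study drug; stable prophylaxis may continue.

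No primary or secondary result, alpha or power is touched. The negative change categories are close to redundant rather than harmful.

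**What to change.** 1. **Form.** On the End of Treatment S-STS, for non-zero items only, add an entry for whether the item occurred before the dose, after it, or both. The eDiary holds the dose date and time as the reference.
2. **SAP section 5.7.6.6 and Table 3.** Report per arm the number and percentage of treated subjects with any post-dose score above 0, for ideation, behavior and total. List pre-dose positives separately with the dose date. Align the population: Table 3 names all treated subjects, while Appendix 1 lists Table 14.2.3.8.11 for mITT subjects.
3. **If the form can no longer be changed.** SAP Appendix 3 is written in the past tense, so this is possible. In that case report any score above 0 per arm, list each case with dose and visit dates, and do not label undated events treatment-emergent.
4. **Separately,** reconcile the during-the-study wording of exclusion 6e with Protocol section 6.2.5. One refers to any score above 0, the other to the investigator's judgment of risk, and a score obtained after dosing cannot act as an entry criterion.

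The cost is one extra entry for the few subjects with a non-zero item, plus reliance on their recall of timing. The scale is not scored twice for everyone, and the table becomes simpler.

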4.3.1 Screening Phase (3-28 days)

It is estimated that approximately 1415 patients will be screened to allow 1200 patients to be randomized at the Baseline visit. All patients who are screened into the study will be entered into the IWRS system. After obtaining informed consent, patients will undergo all screening procedures as detailed in [Table 1](#). After all screening procedures are complete, patients will return 3-28 days from signing informed consent to be randomized at the Baseline visit if they meet all eligibility criteria. Patients on prophylactic migraine medication are permitted to remain on therapy provided they have been on a stable dose for at least 3 months prior to randomization.

4.3.2 Acute (Randomization) Phase (45 days)

If the patient meets all eligibility criteria they will be randomized at the Baseline Visit via the IWRS system. The patients will be provided with an eDiary. The study personnel will instruct the patient on the proper use of the eDiary and ensure proper understanding and use of the tool, prior to the patient leaving the office.

After randomization via the IWRS system, the patient will be dispensed a single dose of the double-blind study medication to take home for up to 45 days. This study medication is to be taken when a migraine attack reaches moderate or severe intensity on the numeric rating scale (NRS) as indicated in the eDiary. The patient will be instructed to take their study medication, as an outpatient, when (if) they have a migraine headache which reaches moderate or severe intensity **after they answer eDiary questions about their current pain and symptoms and identify their currently most bothersome, migraine associated, symptom (phonophobia, photophobia or nausea)**. The patient will complete an eDiary for up to forty-eight hours after taking study medication. The patient will telephone the study center immediately if a severe or serious adverse event occurs.

Patients will record efficacy data in their eDiary. This includes the following: onset time of headache, intensity of the headache prior to **and** at time of taking study medication. The patient should record all headache intensity leading up to dosing, but should not dose with study medication until the headache reaches moderate or severe intensity. Headache severity will be recorded using a four-point numeric rating scale (no pain, mild pain, moderate pain, severe pain) at the onset of the migraine and after dosing at time points of 15, 30, 45, 60, and 90 minutes and 2, 3, 4, 6, 8, 24 and 48 hours. The presence or absence of associated symptoms (nausea, photophobia, phonophobia) and ratings of functional disability (four-point scale: normal, mildly impaired, severely impaired, requires bedrest) will be recorded at the same time points as the headache severity ratings. Patients will also identify their currently most bothersome symptom before taking study medication. Patients will record the date and time study therapy was taken in their eDiary. Patients will also complete the migraine-specific quality-of-life questionnaire (MQoLQ) and preference of medication (PoM) 24 hours after

dosing. Patients who have headache pain reduced to a mild intensity or pain free intensity level will be considered to have achieved pain relief.

After dosing with study medication, all other headache medication is prohibited during the 2 hours post dose. However, a patient who does not experience relief of their migraine headache at the end of two hours after dosing with study medication (and after the two hour assessments have been completed on the eDiary) will be permitted to use the following rescue medication: aspirin, ibuprofen, acetaminophen up to 1000mg/day (this includes Excedrin Migraine) naproxen (or any other type of nonsteroidal anti-inflammatory (NSAID)), antiemetics (e.g., metoclopramide or promethazine), or baclofen. These are the only medications allowed for rescue treatment after 2 hours post dose of study medication. However, if needed, after 48-hours of administering the one dose of study medication (and before returning for the End of Treatment Visit) patients may take their prescribed standard of care medications for treatment of migraine, including triptans if not contraindicated, **provided all of the assessments have been completed on the eDiary**. Exclusionary rescue medication such as, opioids, ergotamines, butalbital compounds, and muscle relaxants (except baclofen as a rescue medication, see above) are not allowed on this study. Similarly, if the migraine is relieved by study medication at 2 hours after dosing but then recurs to a moderate or severe intensity level between two and forty-eight hours, the patient will be permitted to take the same rescue therapy as outlined above. In all circumstances, the patient will continue to complete his or her eDiary for up to forty-eight hours after consuming the study medication.

